Cover Letter – Protocol Registration and Results System (PRS)

Date: Dec.13.2025

To:

Protocol Registration and Results System (PRS) Review Team

Subject: Protocol Registration Submission

Dear PRS Review Team,

We respectfully submit the study protocol entitled **“Application of Growth Factors Derived from Platelets to Accelerate Healing and Reduce Post-extraction Complications in Diabetic Individuals”** for registration in the Protocol Registration and Results System (PRS).

This protocol describes a **randomized, double-blinded, split-mouth clinical trial** that will be conducted at King Abdulaziz University Dental Hospital. The study is designed to evaluate the effect of **Advanced Platelet-Rich Fibrin (A-PRF)** on post-extraction soft tissue healing in patients with diabetes mellitus, a population known to exhibit impaired wound healing and increased susceptibility to postoperative complications.

The study will enroll adult diabetic patients requiring bilateral extraction of the same tooth type. One extraction socket will be randomly assigned to receive A-PRF, while the contralateral socket will serve as a control. Healing will be assessed using **digital intraoral scanning at predefined time points**, along with patient-reported outcome measures. The split-mouth design has been selected to minimize inter-individual variability and improve internal validity.

The protocol has been developed in accordance with ethical and methodological standards for human clinical research. Ethical approval has been obtained from the Institutional Review Board of King Abdulaziz University Dental Hospital, and the study will be conducted in compliance with the Declaration of Helsinki. Written informed consent will be obtained from all participants before enrollment. At the time of registration, no participants have been enrolled, and no data have been collected.

This registration is being submitted to ensure **transparency, methodological rigor, and prospective documentation** of the study design and planned analyses. We confirm that the information provided in the PRS submission accurately reflects the study protocol and that study results will be reported in accordance with PRS requirements upon completion.

Thank you for your review and consideration of this protocol registration. Please do not hesitate to contact us if you require any additional information or clarification.

Sincerely,

[name] [name]

Principal Investigator

King Abdulaziz University Dental Hospital

Jeddah, Saudi Arabia

Email: [your institutional email]

On behalf of the study team:

[name]; [name]; [name]

**Application of Growth Factors Derived from Platelets to Accelerate Healing and Reduce
Post-Extraction Complications in Diabetic Individuals**

Authors

[name]*, [name]*, [name]

Abstract

Introduction

Diabetes Mellitus (DM) represents a significant global public health challenge, with a particularly high prevalence in Saudi Arabia. The increasing incidence of DM has raised concerns regarding optimal management strategies for surgical procedures such as dental extractions. Diabetic individuals frequently experience impaired postoperative healing due to compromised tissue repair mechanisms and increased susceptibility to infection. Conventional management approaches may be insufficient, highlighting the need for biologically driven adjunctive therapies.

Objective

This study aims to evaluate the clinical effectiveness of Advanced Platelet-Rich Fibrin (A-PRF) in enhancing soft-tissue healing and reducing post-extraction complications in diabetic patients.

Methods

A randomized, double-blinded, split-mouth clinical trial will be conducted at King Abdulaziz University Dental Hospital. Diabetic patients requiring bilateral extraction of the same tooth type will be enrolled. One extraction socket will be randomly assigned to receive A-PRF, while the contralateral socket will serve as the control. Healing will be assessed using digital intraoral scanning at baseline, 1 week, and 3 weeks post-extraction. Statistical analysis will be performed using paired-comparative tests, with a significance level of $p < 0.05$.

Expected Outcomes

The application of A-PRF is expected to enhance soft tissue healing and reduce postoperative complications in diabetic individuals.

Conclusion

This study is expected to provide clinical evidence supporting the use of A-PRF as a biologically based adjunctive approach to improve post-extraction healing outcomes in diabetic patients.

Introduction

Diabetes Mellitus (DM) is a global public health problem, with an especially high prevalence in Saudi Arabia. The rising incidence of DM has increased concerns regarding the management of diabetic patients undergoing surgical procedures, including tooth extractions. Diabetic individuals often exhibit impaired postoperative healing characterized by delayed tissue repair,

prolonged inflammation, and an increased risk of infection. Conventional treatment strategies may not adequately address these challenges, necessitating the exploration of novel regenerative approaches.

Platelet-derived growth factors, particularly Advanced Platelet-Rich Fibrin (A-PRF), have recently gained attention as potential promoters of wound healing and tissue regeneration. A-PRF is a biologically active autologous scaffold that aligns with the physiological principles of wound healing by providing a sustained release of key growth factors such as platelet-derived growth factor (PDGF), transforming growth factor- β (TGF- β), and vascular endothelial growth factor (VEGF). These growth factors are essential for cellular migration, angiogenesis, and extracellular matrix remodeling.

In diabetic patients, chronic hyperglycemia, prolonged inflammation, microvascular dysfunction, and impaired collagen synthesis contribute to delayed wound healing. The theoretical premise of A-PRF is that it may enhance the natural healing cascade in diabetic individuals by compensating for impaired biological responses. However, despite promising biological rationale and preliminary clinical evidence, there remains limited high-quality clinical data evaluating the effectiveness of A-PRF in post-extraction socket healing in diabetic patients.

Therefore, this study will aim to evaluate the effectiveness of A-PRF in enhancing soft tissue healing and reducing post-extraction complications in diabetic individuals using a split-mouth randomized clinical trial design. The findings are expected to contribute to evidence-based clinical protocols and improve standards of care for diabetic patients undergoing dental extractions at King Abdulaziz University Dental Hospital.

Research Question

Does the application of growth factors derived from platelets accelerate healing and reduce post-extraction complications in diabetic individuals?

Research Hypotheses

Null Hypothesis (H0):

The application of platelet-derived growth factors will not enhance healing or reduce post-extraction complications in diabetic individuals.

Alternative Hypothesis (H1):

The application of platelet-derived growth factors will accelerate healing and reduce post-extraction complications in diabetic individuals.

Objectives

Using a split-mouth design, this study will evaluate soft tissue closure of extraction sockets by comparing sites treated with A-PRF to sites without A-PRF application at King Abdulaziz University Dental Hospital.

Significance of the Study

1. This research is expected to demonstrate the potential of A-PRF to enhance postoperative healing and improve the quality of life in diabetic patients undergoing dental extractions.
2. The findings may contribute to the development of improved, biologically based treatment protocols for diabetic patients in dental practice.

Literature Review

Diabetes Mellitus (DM) is a complex chronic disease affecting millions worldwide, with a notably elevated prevalence in Saudi Arabia. The increasing incidence of DM has been attributed to lifestyle changes, urbanization, and genetic predisposition. Microvascular complications such as retinopathy, nephropathy, and neuropathy significantly increase morbidity and mortality among diabetic patients.

In oral health, diabetes is associated with delayed wound healing, increased susceptibility to infection, periodontal disease, and tooth loss. The healing of extraction sockets normally progresses through distinct stages, including clot formation, inflammation, proliferation, and remodeling. However, in diabetic individuals, chronic hyperglycemia disrupts these processes by impairing angiogenesis, inflammatory regulation, collagen synthesis, and bone formation.

Platelet-rich fibrin (PRF) has emerged as a regenerative biomaterial capable of enhancing wound healing through sustained growth factor release. Advanced PRF (A-PRF), produced using low-speed centrifugation protocols, retains higher concentrations of platelets and leukocytes within a fibrin matrix. This biological scaffold is expected to improve cellular migration, angiogenesis, and tissue regeneration, making it particularly relevant for diabetic patients with compromised healing capacity.

Despite promising biological mechanisms, there remains limited clinical evidence evaluating the specific role of A-PRF in post-extraction socket healing in diabetic patients, highlighting the need for well-designed randomized clinical trials.

Materials and Methods

Study Design and Ethics

This double-blinded, randomized controlled clinical trial will be conducted at King Abdulaziz University Dental Hospital. Ethical approval has been obtained from the Institutional Review Board, and the study will be conducted in accordance with the Declaration of Helsinki (2013). Written informed consent will be obtained from all participants prior to enrollment.

Sample and Study Population

The sample size has been calculated using G*Power software with an alpha level of 0.05, 80% power, and a medium effect size of 0.5. Diabetic patients aged 18 years or older requiring bilateral extraction of the same tooth type will be recruited. Patients with systemic conditions other than diabetes, bleeding disorders, pregnancy, lactation, or tobacco use will be excluded.

A split-mouth design will be employed, with one extraction site randomly assigned to receive A-PRF and the contralateral site serving as a control. Randomization will be performed using a computer-generated sequence. Patients and outcome assessors will remain blinded throughout the study.

Clinical Procedure

All extractions will be performed using a standardized atraumatic technique by a single calibrated operator. After extraction, venous blood will be collected to prepare A-PRF using a low-speed centrifugation protocol. The A-PRF membrane will be placed into the assigned socket, while control sockets will receive no adjunctive material. All sites will be sutured using standardized suture material.

Outcome Measures

Healing will be assessed quantitatively using digital intraoral scanning at baseline, 1 week, and 3 weeks post-extraction. Patient-reported outcomes, including pain, swelling, and satisfaction, will be collected using validated questionnaires at specified follow-up intervals.

Statistical Analysis

Data will be analyzed using Stata software (Version 16). Normality will be assessed using the Shapiro–Wilk test. Paired statistical tests will be used to compare healing outcomes between A-PRF-treated and control sites, with significance set at $p < 0.05$.

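### Does it undermine the closure comparison that the person suturing is not blinded and only the suture material is standardized for that step?

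*Combined protocol and SAP*

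**What the plan says.** Under Materials and Methods, Sample and Study Population, the plan states "Patients and outcome assessors will remain blinded throughout the study" and, on allocation, "Randomization will be performed using a computer-generated sequence". It does not say who holds the sequence or when the operator learns the side.

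The Clinical Procedure section covers three steps:

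- Extraction: "All extractions will be performed using a standardized atraumatic technique by a single calibrated operator".
- Intervention: "The A-PRF membrane will be placed into the assigned socket, while control sockets will receive no adjunctive material".
- Closure: "All sites will be sutured using standardized suture material".

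The Objectives section says that "this study will evaluate soft tissue closure of extraction sockets by comparing sites treated with A-PRF to sites without A-PRF application". Under Outcome Measures, "Healing will be assessed quantitatively using digital intraoral scanning at baseline, 1 week, and 3 weeks post-extraction". The cover letter gives the reason for the design: "The split-mouth design has been selected to minimize inter-individual variability and improve internal validity".

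**The concern.** Extraction is controlled by technique and by operator. Closure, in the same section, is controlled by material alone. Closure comes after the membrane has gone into one socket and nothing into the other, and neither a sham material nor a separate blinded closer is described. A step that acts on the outcome is therefore done by someone who very probably knows the side, with no common technique written down.

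The plan's two main safeguards do not reach this step. Blinded reading of the scans removes bias in measurement, but not a difference that is already in the tissue. The split-mouth design removes differences between patients, but not unequal handling of one patient's two sides. If the treated socket were closed more carefully, or less so, part of that could appear as a difference in closure at 1 and 3 weeks. Scans can be measured again under a code if the files are kept, whereas suturing cannot be repeated.

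**Working it through.** The question turns mainly on reading the text.

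**1. Is the blinding statement wrong?** The plan calls the trial double-blinded and then names two blinded parties, patients and outcome assessors. That is a common meaning of the term. The operator's absence from the list is consistent with the comparison, since whoever places the membrane sees it. There is no contradiction.

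**2. Is closure uncontrolled?** Not wholly. One sentence covers all sites alike, and it gives no different instruction for treated and control sockets. What it lacks is technique. The standardized technique and single operator are stated for extraction only. Who sutures is not stated, so the claim that this person sees the side is an inference, though a strong one.

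**3. What kind of difference would bias the result?** The side is assigned at random. A habitual left-right difference in suturing would therefore fall on either treatment by chance and would not favour one systematically. Only handling that follows the allocation could bias the comparison. The documents neither describe nor imply such handling.

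**4. Would it carry through to the result?** Possibly, in part. The plan does not say whether the baseline scan comes before or after suturing, or whether healing is analysed as change from baseline. If the scan follows suturing and change is analysed, an initial difference in closure is at least partly accounted for. A baseline difference might also come from the membrane itself and so belong to the treatment.

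**5. How large could it be?** The documents give no bias size and no sample size, so there is no figure of the plan's to reproduce. The stated inputs are effect size 0.5, alpha 0.05 and power 80%. I assume a two-sided paired t-test, with 0.5 as the standardized paired difference. Power is then P(|T| > t(0.975, n−1)), where T is noncentral t with n−1 degrees of freedom and noncentrality 0.5√n. It is 79.5% at n = 33 and 80.8% at n = 34, so n = 34.

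With no true effect and a constant shift b toward A-PRF, the noncentrality is b√34 = 5.831b:

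| Assumed b (SD of paired difference) | Noncentrality | Rejection rate, two-sided |
|---|---|---|
| 0 | 0 | 5.0% |
| 0.1 | 0.583 | 8.7% |
| 0.2 | 1.166 | 20.5% |
| 0.3 | 1.749 | 39.7% |

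These rates show only that a constant bias inflates false positives, as it would in any trial. The values of b are invented for illustration and say nothing about whether suturing here will differ by side.

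**6. What would an amendment achieve?** It could state that one technique, of the investigators' choosing, is used on both sides. It could also state when the side is released. The first records what a standardized procedure would normally entail. The second protects extraction and does not reach suturing. The suturing step would remain unblinded after both.

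**The case for a change.** The strongest contrary case is that, because the operator cannot be blinded, a common suturing technique is the one control left, and the plan omits it where the outcome is most exposed. The protocol shows with extraction that it knows how to write such a control. The single-operator sentence does not cover suturing, and a single operator who knows the side can still treat the sides differently. The cover letter says that nobody had been enrolled at registration, so a few sentences then would have cost almost nothing.

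Most of this is factually right. For closure only the material is fixed, the person suturing is not listed as blinded, and blinded scan reading would not undo a difference made at surgery. A sentence on technique would be a reasonable courtesy to readers. What does not stand is the step from an unstated technique to a defect in the design. The protocol is brief and leaves many operative details unwritten. Its silence on suturing technique is of the same kind as its silence on allocation concealment, patient masking and scan coding: missing detail, not evidence of unequal handling or failed blinding. Asking for masked patients and coded scans would largely restate the blinding to which the plan already commits.

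**Conclusion.** No change to the plan is needed. The observation is accurate when limited to closure: only the suture material is standardized there, and the person suturing very probably knows the side. Side-related suturing could contribute to a difference between sockets, but the documents do not show that it will.

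The lack of operator blinding is inherent in comparing a membrane with an empty socket, and it is properly handled by saying so when the trial is reported. The unstated technique is a gap that a trial team fills sensibly in practice. No size can be attached to the effect, because the illustrative error rates depend entirely on assumed shifts and an inferred sample of 34 pairs.

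This conclusion assumes that the blinding of patients and assessors is kept as stated and that the closing instruction for all sites is applied alike to both sides. Evidence that the sides were closed differently according to allocation would reopen the question.

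### Does leaving the baseline scan and the disclosure of the treated side unplaced in the surgical sequence undermine the split-mouth comparison?

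*Combined protocol and SAP*

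**What the plan says.** Clinical Procedure (Materials and Methods) gives an order of events. First come the extractions: "All extractions will be performed using a standardized atraumatic technique by a single calibrated operator". Then: "After extraction, venous blood will be collected to prepare A-PRF using a low-speed centrifugation protocol". Then: "The A-PRF membrane will be placed into the assigned socket, while control sockets will receive no adjunctive material". Finally: "All sites will be sutured using standardized suture material".

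Outcome Measures gives the scan schedule, "Healing will be assessed quantitatively using digital intraoral scanning at baseline, 1 week, and 3 weeks post-extraction", and the Methods part of the Abstract repeats it. Neither places the baseline scan within the surgical order. The cover letter adds nothing on this.

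The Objectives section names the target: "this study will evaluate soft tissue closure of extraction sockets by comparing sites treated with A-PRF to sites without A-PRF application". Statistical Analysis says "Paired statistical tests will be used to compare healing outcomes between A-PRF-treated and control sites" and does not mention change from baseline.

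Sample and Study Population states that the sequence is computer-generated and that patients and outcome assessors are blinded throughout. It does not say who holds the sequence, when the side is revealed, or whether the operator is blinded.

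**The concern.** A split-mouth comparison depends on the two sockets being created and measured in the same way. Pairing removes differences between patients. It does not remove an error that falls on one side only.

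Three readings of baseline are open:

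- **Before extraction:** there is no socket opening to measure.
- **After extraction, before placement:** the two sides are comparable.
- **After placement:** the treated side may already look different, because the control socket receives nothing.

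Under the third reading, closure calculated from baseline could be biased, and the image might show the assessor which side was treated.

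Separately, an operator who knows the side before extracting could be gentler, or less gentle, on one side. Drawing blood after extraction makes late disclosure possible but does not require it. Early disclosure could not be undone in the analysis.

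**Working it through.** The plan gives no figure on this point and no sample size, so there is nothing to reproduce. The check is a reading of the text plus two illustrations. All error sizes below are assumed.

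**1. When does scan timing matter?** A baseline scan can bias the treatment comparison only if (a) it is taken after placement and (b) the outcome is calculated from it. The plan states neither. The planned paired comparison of healing between sites can be run directly on the 1-week and 3-week openings, and baseline then drops out.

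**2. How large could the distortion be if both conditions held?** Assumptions: a true opening of 100 mm² on each side; closure = 1 − R / [100 × (1 − m)], where R is the remaining opening and m is the share of the treated opening that the membrane hides at baseline; m = 0 on the control side.

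| Case | m = 0.10 | m = 0.20 | m = 0.30 |
|---|---|---|---|
| Treated, true closure 60% (R = 40) | 1 − 40/90 = 55.6% | 1 − 40/80 = 50.0% | 1 − 40/70 = 42.9% |
| Treated, true closure 70% (R = 30) | 1 − 30/90 = 66.7% | 1 − 30/80 = 62.5% | 1 − 30/70 = 57.1% |
| Second row minus control at 60% | +6.7 points | +2.5 points | −2.9 points |

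The true 10-point benefit disappears at m = 1 − 30/40 = 0.25. At 3 weeks, with true closure of 90% on both sides (R = 10) and m = 0.20, treated closure reads 1 − 10/80 = 87.5%, an error of 2.5 points. In every case the error works against A-PRF. The protocol places the membrane into the socket and sutures every site. It does not say that the membrane covers the opening. If closure is measured at the soft-tissue margin, which is also unstated, m could be close to zero.

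**3. What could unequal handling do?** Inputs from the plan: alpha 0.05, power 80%, effect size 0.5. With an exact paired t-test (noncentral t), reading 0.5 as the standardized paired difference gives 34 pairs two-sided (power 80.8%) or 27 one-sided (81.2%). Reading it as a between-site effect with zero correlation gives 0.5/√2 = 0.354 and 65 pairs two-sided. With no true effect and a systematic shift in SDs of the paired difference, two-sided rejection at the 5% level is:

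| Pairs | Shift 0.1 SD | Shift 0.2 SD |
|---|---|---|
| 34 | 8.7% | 20.5% |
| 65 | 12.5% | 35.5% |

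For a trial sized one-sided at 27 pairs and tested one-sided, the rates are 12.7% and 26.4% if the shift favours A-PRF, and 1.6% and 0.4% if it goes the other way. These figures describe any paired trial with a shift of that size. Nothing in the documents ties such a shift to this operator or this scan.

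**4. What does the plan already limit?** Each patient contributes both sites, so knowing the side in advance cannot put different patients into the two arms. One calibrated operator, one standardized technique and standardized sutures narrow the room for unequal handling. Assessor blinding is an explicit commitment, although its mechanism is not described.

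**The case for a change.** The strongest case for a change is that the cover letter reports no one enrolled, a few sentences would settle everything, and some losses would be permanent. Taking baseline to mean before treatment still leaves two readings, and a scan before extraction shows no open socket. The operator is not listed as blinded, and extraction technique can affect the wound itself. A blinding commitment without a procedure is also weaker than one with a procedure.

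Much of this stands as description. Scan timing, use of baseline, custody of the sequence and coding of scans are all unwritten, and an early disclosure of the side cannot be repaired afterwards. The claim of permanent loss does not hold for the baseline scan, because comparing follow-up openings directly avoids the bias altogether. Nor do the documents show that the membrane is visible after suturing or that the operator knows the side early. Coding the files would not hide a membrane still visible in a 1-week image, so the obvious remedy would be only partial.

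**Conclusion.** No change to the plan follows. These are gaps in description that a competent team would fill in the ordinary way: a pre-treatment baseline, assessors kept unaware of the side, and a paired comparison of the two sites. No stated rule produces a wrong result.

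The baseline bias is zero unless a post-placement scan and closure calculated from it occur together. If they did, the illustration puts the loss at 3.3 to 12.9 points of a true 10-point benefit at 1 week for 10% to 30% hidden area, always against A-PRF. That rests on an assumed closure formula and an assumed hidden area. The remaining point is possible unequal handling by an operator who knows the side. Its size is unknown, and the single calibrated operator and standardized technique limit it without excluding it. The harms are possible, not shown. Scan timing, custody of the sequence and coding of scans are matters for the site's working procedures.

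### Does leaving open whether pain, swelling and satisfaction are scored by site or by patient undermine the split-mouth comparison?

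*Combined protocol and SAP*

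**What the plan says.** Under Sample and Study Population, each patient contributes both treatments, with "one extraction site randomly assigned to receive A-PRF and the contralateral site serving as a control". Eligible patients are those "requiring bilateral extraction of the same tooth type will be recruited". The section does not say whether the two extractions share a visit or are staged. It does say that "Patients and outcome assessors will remain blinded throughout the study".

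Patient-reported outcomes appear in two places. Outcome Measures states: "Patient-reported outcomes, including pain, swelling, and satisfaction, will be collected using validated questionnaires at specified follow-up intervals". The cover letter mentions them in the sentence on how healing will be assessed, beside the digital scan. Neither place gives the unit of recording, the instruments or the times.

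On analysis, the Statistical Analysis section says "Paired statistical tests will be used to compare healing outcomes between A-PRF-treated and control sites". The Abstract plans paired comparative tests without tying them to an outcome; the only assessment its Methods describe is the scan: "Healing will be assessed using digital intraoral scanning at baseline, 1 week, and 3 weeks post-extraction".

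The Objectives section commits to one comparison: "this study will evaluate soft tissue closure of extraction sockets by comparing sites treated with A-PRF to sites without A-PRF application". The alternative hypothesis is broader: "The application of platelet-derived growth factors will accelerate healing and reduce post-extraction complications in diabetic individuals".

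**The concern.** In a parallel-group trial one questionnaire per patient belongs to one arm, so the unit of recording rarely matters. Here every patient is in both arms. A scan of a socket is site-specific by nature, but a questionnaire is answered by a person. Asked how much pain there has been, a patient with two healing sockets may give one answer covering both. Satisfaction is even more naturally a whole-patient rating.

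If that happened, these outcomes would carry no information on A-PRF versus control, and a side that was never recorded cannot be added later. The hypothesis includes fewer complications, and pain, swelling and satisfaction are the only outcomes specified beyond the scan. They are therefore the only measures that might bear on that part of it, although the document never defines complications in those terms. The paired tests are promised for healing outcomes, and Outcome Measures describes healing by scan and lists patient-reported outcomes separately. Read strictly, these outcomes have neither a recording unit nor an analysis.

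**Working it through.** There is no stated figure to reproduce: the document gives an alpha, a power and an effect size but no sample size, and this point does not depend on one. The check is which forms of recording would yield the contrast, and which of them the document points to.

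**Setup.** Let *A* be the mean score attributable to the A-PRF site and *C* the mean attributable to the control site. The target is *A* − *C*, that is, weights (1, −1) on (*A*, *C*). It can be estimated only if those weights can be built from what is recorded.

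**1. One whole-mouth score while both sites heal.** Assume both sides weigh equally, so the score is 0.5*A* + 0.5*C*, with weights (0.5, 0.5). A multiple *k* of this row would have to satisfy 0.5*k* = 1 and 0.5*k* = −1, so *k* = 2 and *k* = −2 at once. That is impossible, and the difference is not estimable at any sample size. If the sides weighed unequally the weights would be unknown, and there would still be no within-patient pair.

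**2. A score for each side.** The rows are (1, 0) and (0, 1). The first minus the second is (1, −1), so each patient gives one pair and a paired test applies.

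**3. One comparative item (which side was worse, or preferred).** This is a single answer per patient, but it bears on the difference directly: its row is (1, −1). Two scores per patient are therefore not strictly necessary.

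**4. Staged extractions with a questionnaire after each.** If each questionnaire refers to one healing site, the rows are again (1, 0) and (0, 1), as in case 2.

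So one form out of four fails. The failure is complete for the outcome concerned; the other three keep the contrast.

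**Which form does the document point to?**

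| Place | What it fixes | Bearing on the unit |
|---|---|---|
| Sample and Study Population | Site is the randomised unit; patient blinded | A side rating gives a fair contrast |
| Cover letter | Patient-reported measures sit within the healing assessment | Brings them under healing outcomes |
| Statistical Analysis | Paired tests of healing outcomes between sites | Needs data by side, or a side comparison |
| Abstract | Paired tests for the analysis as a whole | Same |
| Outcome Measures | Names the three outcomes; unit not given | Neutral |

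No line states or implies a whole-mouth score. The lines that bear on the matter favour recording by side, though none settles it.

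**Burden.** Questionnaire times are not given. Assuming two (1 and 3 weeks, as for the scan), pain and swelling need 2 outcomes × 2 times = 4 ratings per patient if asked once, and 4 × 2 sides = 8 by side. With satisfaction included the figures are 3 × 2 = 6 and 6 × 2 = 12. At that size, workload is no reason for the team to choose the form that fails.

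**The case for a change.** The strongest argument for a change is that silence is risky when the error cannot be repaired. A split-mouth design guarantees site-level scans but not site-level questionnaires, and validated forms are often written for the whole patient. Outcome Measures separates healing from patient-reported outcomes, so the paired tests may not have been meant for them; and if they were, a paired test does not by itself secure paired data. The cover letter reports that nobody had been enrolled at registration, so a clarifying sentence would cost almost nothing.

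Much of this stands. The omission is real, it is not explained by removed or redacted text, and a whole-mouth score would leave these outcomes unable to support a treatment comparison. Satisfaction is the most exposed, since an overall rating cannot be assigned to one socket. Asking by side also has a price, because per-side items may depart from the validated form.

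What does not stand is the step from an unstated detail to a faulty design. The harm depends on a choice that the document does not make and that its paired, site-based structure argues against. The claim that no analysis exists is also too strong: a paired between-site analysis is stated generically, and the cover letter allows it to be read as covering these outcomes. Nor would settling the recording unit alone make the complications part of the hypothesis testable, since complications are never defined as these outcomes and infection, which the document names as a risk, is not among the listed measures.

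**Conclusion.** The concern does not call for a change to the plan. The protocol omits the recording unit, the timing and an outcome-specific analysis for pain, swelling and satisfaction, but this is a gap in detail that the team can be expected to fill in a way consistent with its own design.

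The consequence has two possible sizes. If a whole-mouth score is taken while both sites heal, all of the A-PRF versus control information in that outcome is lost. If the outcome is recorded by side, by a comparative item, or after each of two staged extractions, the contrast is kept. The soft tissue closure objective is measured by scan at each site and is untouched in every case.

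The conclusion rests on two assumptions: that the questionnaire forms, which are not in the document, follow the site-by-site logic of the design, and that any whole-mouth satisfaction score is reported as a description and not as a treatment effect. Forms showing a single whole-mouth rating of pain and swelling with both sites healing would overturn it for those outcomes.
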